14.1 Primary Aim

The primary aim is to compare the PUSH Plus Protein study subjects (n=30) to those who received PUSH from CAP (n=105). The primary outcome is the distance walked in six minutes (6MWT). Previous analyses of various physiologic measures in the Baltimore Hip Studies data ("BHS"; data unpublished) have shown a $r>0.80$ within subject correlation of measures across time. Preliminary data from CAP-MP have shown a within subject correlation of $r=0.78$ for initial subjects in usual walking speed (n=13).

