14.2 Secondary Objectives

A longitudinal analysis using Generalized Estimating Equations (GEEs) will be employed. A model of the form $Y(t) = a + b_1 X + b_2 t_4 + b_3 X t_4$ will be used where: $Y(t)$ is the dependent variable Y at time t (which is 0 or 4 months post baseline testing); a is the intercept; X is an indicator variable for treatment group (PUSH vs PUSH+ Protein); t_4 is an indicator variable for time at 4 months post baseline testing; $X t_4$ is an interaction term for treatment and time; and b_1 through b_3 are empirically derived regression coefficients. An unstructured covariance matrix, an identity link function, and robust standard errors will be used. The effect of intervention on each mechanistic factor will be assessed by estimating the magnitude of the coefficient b_3 , which is interpreted as mean change in outcome from baseline to 4 months comparing PUSH Plus Protein to PUSH alone. The primary outcome will be the 6-minute walk test (6MWT). Other potential outcomes include: activities of daily living (ADLs), quality of life, lower-extremity physical performance, increase of ≥ 50 meters in distance walked in six minutes, cognitive status, and nutritional status.

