14.4 Sample Size Adequacy

Power analyses were conducted for detectable mean changes from baseline (conservatively) assuming a within subject correlation of $r=0.70$. For between group differences, assuming 10% loss to follow up from all causes (mortality, attrition, etc.) by 16 weeks post randomization (CAP n=105 in the PUSH arm and this study will have n=30, so effective n=94 compared to n=27 including attrition). The study will have 80% power to detect differences of 0.475 standard deviations assuming two-sided tests and an alpha level of 0.05. These differences are considered small-to-moderate effects using Cohen's criteria for interpretation of effect sizes (where 0.2 is "small" and 0.5 is "medium"). Given a 6MWT mean of 186.7 and SD=55.8 in the most recent overall sample from CAP (n=199, DSMB report May 2017), this would translate into a difference of 22.9. Similar magnitude of effects (SD=0.41) are detectable comparing to other measures available in the CAP study (e.g, SPPB, 3MS, etc.).

For outcomes only available in the CAP-MP study, the comparison sample is 19 subjects in CAP-MP PUSH. Assuming 10% loss to follow up (n=17 in CAP-MP PUSH group vs n=27 in pilot study), the study will have 80% power to detect between group differences of 0.62 standard deviations assuming two-sided tests and an alpha level of 0.05. This is considered a moderate-to-large effect size by Cohen.

Section 15: Data Capture, Data Management, and Quality Assurance

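### The only specified model compares raw change; a baseline-adjusted estimate should be prespecified beside it, and the CAP-MP power figure matched to the model chosen

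*Protocol*

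**What the plan says.** Protocol 14.1 names the primary comparison (30 pilot participants against 105 from the PUSH arm of CAP) and the six-minute walk distance as its outcome, but gives no model. The model appears in 14.2 and is repeated in the SAP under Secondary Objectives: "A model of the form $Y(t) = a + b_1 X + b_2 t_4 + b_3 X t_4$ will be used". Although headed as secondary, that section names the six-minute walk as the primary outcome. The effect is b3, "which is interpreted as mean change in outcome from baseline to 4 months comparing PUSH Plus Protein to PUSH alone".

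No baseline covariate is specified in either document. Marginal structural modelling is mentioned in 14.3 only as something the missing-data weights could be combined with; no covariates are given for it. The baseline walk is a required measure (Protocol 10.1).

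Protocol 14.4 computes power "assuming a within subject correlation of" 0.70, with group sizes "so effective n=94 compared to n=27 including attrition". It states 0.475 SD as detectable against CAP and 0.62 SD against CAP-MP (17 vs 27). Protocol 14.1 also reports that unpublished physiologic measures "have shown a $r>0.80$ within subject correlation of measures across time", and gives 0.78 for usual walking speed in 13 CAP-MP subjects.

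**The concern.** With two visits, complete pairs, an unstructured covariance and a free group term, b3 is the difference between groups in mean raw change. That choice has two consequences.

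The first is precision. A regression of the 16-week value on group and baseline value uses the same data and, when the groups are exchangeable, never has larger variance in large samples. The comparator studies are complete, so their numbers cannot grow, and the analysis is the cheapest place to recover precision.

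The second is the handling of a baseline gap. Raw change assumes that a gap carries over to 16 weeks one for one. The adjusted estimate assumes that it carries over in proportion to the regression slope. For a single-site cohort set against a three-site external arm (Protocol 3 and 4.1), the gap may be chance or systematic, and the two estimates can then give different answers. The plan neither justifies relying on change alone nor offers a sensitivity analysis. Sections 14.3 and 14.4 speak of randomisation, which this design does not have.

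**Working it through.** **Inputs.** Protocol 14.4: r = 0.70, SD 55.8, n = 94 vs 27 (CAP) and 17 vs 27 (CAP-MP), two-sided alpha 0.05, 80% power. Protocol 14.1: r = 0.78 and r > 0.80. Multiplier 1.960 + 0.842 = 2.802.

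**Formulas, equal SDs at both visits.** SE in SD units = √f × √(1/n1 + 1/n2), with f = 2(1 − r) for raw change and f = 1 − r² for the baseline-adjusted contrast. Detectable difference = 2.802 × SE. Variance ratio, adjusted to change = (1 − r²)/[2(1 − r)] = (1 + r)/2.

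**Step 1: the plan's CAP figure.** √(1/94 + 1/27) = 0.2183. Raw change at r = 0.70: 2.802 × √0.60 × 0.2183 = 0.474 SD, and power at 0.475 SD is 80.2%. The stated 0.475 SD reproduces, and it is a change-score figure. The adjusted factor gives 2.802 × √0.51 × 0.2183 = 0.437 SD; a comparison of follow-up values alone gives 0.612 SD.

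**Step 2: six-minute walk in metres.** 55.8 × 0.2183 = 12.18 m, multiplied by √f:

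| r | SE, change | SE, adjusted | Detectable, change | Detectable, adjusted | Variance saved |
|---|---|---|---|---|---|
| 0.70 | 9.44 | 8.70 | 26.4 | 24.4 | 15% |
| 0.78 | 8.08 | 7.62 | 22.6 | 21.4 | 11% |
| 0.80 | 7.71 | 7.31 | 21.6 | 20.5 | 10% |

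At r = 0.70, power at 0.475 SD rises from 80.2% to 86.1%. Simulation of 10,000 trials at 94 vs 27 with equal expected baselines gave variance ratios of 0.84, 0.89 and 0.90, against 0.85, 0.89 and 0.90 from the formula.

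**Step 3: unequal SDs.** Let k be the 16-week SD divided by the baseline SD. The variance saved becomes (1 − rk)²/(1 + k² − 2rk). The documents give no SD by visit, so k is an assumption. At r = 0.70:
- k = 1.0: 0.0900/0.60 = 15%
- k = 1.1: 0.0529/0.67 = 8%
- k = 1.2: 0.0256/0.76 = 3%
- k = 1.3: 0.0081/0.87 = 1%

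A k above 1 is plausible, because anyone who walks 300 m or more at baseline is excluded (Protocol 7.2 and 9.2) and no such ceiling applies at 16 weeks.

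**Step 4: a baseline gap D, equal SDs.** If D is sampling error, b3 shifts by −(1 − r)D. One standard error of D is 12.2 m, which moves b3 by 0.30 × 12.2 = 3.7 m at r = 0.70 and 0.20 × 12.2 = 2.4 m at r = 0.80. If D is a stable difference between cohorts that change equally, b3 is unbiased and the adjusted estimate is biased by (1 − r)D. For an assumed gap of 0.3 SD (16.7 m) at r = 0.70 that bias is 5.0 m, or 0.09 SD, which simulation confirms.

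**Step 5: the CAP-MP figure.** √(1/17 + 1/27) = 0.3096. Raw change at r = 0.70: 2.802 × √0.60 × 0.3096 = 0.672 SD, with 73.4% power at 0.62 SD. Adjusted: 2.802 × √0.51 × 0.3096 = 0.619 SD, with 80.1% power at 0.62 SD. The stated 0.62 SD therefore matches the adjusted variance, while the stated 0.475 SD matches the change-score variance. The planned model would reach 0.62 SD only if 2(1 − r) = (0.62/(2.802 × 0.3096))² = 0.511, that is r ≈ 0.74, which 14.4 does not assume.

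**The case against.** The strongest objection is that the case for adjustment comes from randomised trials. Here all pilot participants receive the intervention (Protocol 6.1) and the comparator is an arm of a completed study. If the cohorts differ stably at baseline, b3 is the unbiased estimate and the adjusted one is not. With the assumed 0.3 SD gap, the adjusted estimate's root mean squared error is about √(8.70² + 5.0²) = 10.0 m, worse than 9.44 m for b3. The break-even gap is √(9.44² − 8.70²)/0.30 ≈ 12.2 m, or 0.22 SD. This stands, and it rules out presenting adjustment as a free gain in efficiency. It also rules out constraining the baselines to be equal.

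The size of the gain is also uncertain. The 0.78 and > 0.80 correlations are not for the six-minute walk, and 0.70 is a deliberately conservative planning value. Above 0.80 the saving is below 10% even with equal SDs, and step 3 shows that it can nearly vanish. This stands too.

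Three stronger readings are tempting, and the documents do not support them:
- A reader might infer that the CAP comparison is underpowered by its choice of model. It is not in SD units, because 0.475 SD already uses the change-score variance. The metre conversion in 14.4 (22.9, where 0.475 × 55.8 = 26.5) is a separate matter and is not relied on here.
- A reader might infer that b3 is wrong and should be replaced. Nothing in the documents shows that comparability given baseline is more credible than equal underlying change.
- A reader might infer that chance imbalance is the main threat. In an external comparison, systematic imbalance is at least as much in question.

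What the objection does not answer is the absence of any stated reason for relying on change alone, or of a second estimate to show whether the conclusion depends on that choice.

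**Conclusion.** The point holds as a gap in prespecification with a modest cost in precision. The planned analysis of the six-minute walk is a raw-change comparison. Under equal visit SDs and exchangeable groups it carries more variance than a baseline-adjusted contrast: the saving from adjusting is 15% of the change-score variance at r = 0.70 and 10–11% at r = 0.78–0.80. It is less if r exceeds 0.80 or the follow-up SD is larger than the baseline SD (8% at a ratio of 1.1 and 3% at 1.2, r = 0.70). The best case within the plan's own figures is an 8% smaller standard error.

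The more important issue is that the two estimates rest on different untestable assumptions in a non-randomised comparison, and the plan commits to one without saying why.

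Separately, the power section mixes two variance assumptions. At its stated correlation, the CAP-MP figure does not belong to the model the plan specifies.

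**What to change.** In Protocol 14.2 and the SAP (Secondary Objectives), for the six-minute walk and every continuous outcome with a baseline value:

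1. Add a regression of the 16-week value on treatment group and baseline value, with identity link, robust standard errors and the missing-data weights already planned. Keep b3 from the present model.
2. State before analysis which of the two is primary and which is the sensitivity analysis, with the reason in terms of the assumption each makes about the external CAP cohort.
3. Report both, with the baseline means and the SD at each visit by cohort, so that a reader can see why they agree or differ.

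In Protocol 14.4 and the SAP (Sample Size Adequacy), state which variance the CAP-MP figure uses. If b3 is primary, then at r = 0.70 and 17 vs 27 the detectable difference should read 0.67 SD, with 73% power at 0.62 SD. If the baseline-adjusted estimate is primary, 0.62 SD can stand for CAP-MP and the CAP figure becomes 0.44 SD.

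The cost is one model line and some wording, with no new data, visits or participants. The downside is that two estimates may disagree, which is why the primary one has to be named in advance. Adjusting for baseline walking distance does not deal with other differences between the cohorts.

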6.1 Overview of Study Design

A pilot study including 30 older adults who have experienced a hip fracture will be carried out with participants receiving a specific multi-component intervention with protein supplementation (PUSH Plus Protein). Study activities for participants meeting eligibility criteria will take place after post-acute rehabilitation ends, up to 26 weeks after admission to the hospital for hip fracture. Patients age 60 and older who have had surgical repair for hip fracture will be identified in study hospitals or by self-referral and evaluated for eligibility. Following consent to participate, eligible participants will undergo a comprehensive baseline assessment. Participants completing the baseline assessment will be eligible to receive the intervention. All participants will receive the PUSH Plus Protein intervention. The follow-up assessment will occur after the intervention is completed, approximately 16 weeks after baseline testing. Figure 1 shows the sequence of participant contacts from the time of hospitalization until the 16-week assessment.

Figure 1. Timeline for screening and follow-up

Within a week of complete baseline testing, the physical therapist (PT) will initiate the exercise intervention and the protein supplement in the home setting. Participants will also receive counseling with a registered dietitian. The follow-up assessment will take place 16 weeks after baseline testing. Telephone interviews will be conducted every four weeks, beginning four weeks after baseline testing, to obtain information about RAEs and expected AEs, and to help reduce loss to follow-up by maintaining ongoing rapport with participants. An honorarium will be given at the completion of both study assessment visits.

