9.4 Improvement in Walking

Whether or not there was an increase of at least 50 meters in the distance walked on the SMWT will be assessed as a tertiary outcome. This distance has been shown to be clinically meaningful.^{142,160}

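### The 50 m responder outcome exists only at follow-up, so the planned two-time-point GEE either cannot identify its effect or returns a crude risk difference with no adjustment for starting distance

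*Protocol*

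**What the plan says.** Protocol section 14.2 sets out the analysis: "A longitudinal analysis using Generalized Estimating Equations (GEEs) will be employed". The model is Y(t) = a + b1·X + b2·t4 + b3·X·t4. X marks the treatment group, t4 marks the 4-month visit, and time is described as "which is 0 or 4 months post baseline testing". The fitting choices are "An unstructured covariance matrix, an identity link function, and robust standard errors will be used". The treatment effect is b3, "interpreted as mean change in outcome from baseline to 4 months comparing PUSH Plus Protein to PUSH alone". No covariates enter the model.

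The same paragraph names the six-minute walk distance as the primary outcome. It then lists further potential outcomes, among them "increase of ≥ 50 meters in distance walked in six minutes". The SAP repeats this text under Secondary Objectives.

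Protocol section 9.4 defines the responder outcome as "Whether or not there was an increase of at least 50 meters in the distance walked on the SMWT" and ranks it as tertiary. The Executive Summary lists it with the secondary outcomes. Neither document gives it a model of its own, a rule for its value at baseline, or an adjustment for starting distance.

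The comparison is not randomised. Section 6.1 states: "All participants will receive the PUSH Plus Protein intervention". The comparator is the PUSH arm of the completed CAP trial. The only weighting specified (section 14.3) is for missing follow-up. Marginal structural modelling is mentioned there as something that could be combined with those weights, but no weight for study source and no covariates are given.

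**The concern.** A gain of at least 50 m is computed from the baseline and follow-up distances together, so each person has one value and Y(0) does not exist. The plan assigns this outcome to a model that needs Y(0). The analyst must then choose, possibly after seeing the data, whether to invent a baseline value, drop the baseline rows or use another model, and whether to adjust for starting distance.

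The obvious workaround, coding the baseline value as 0, leaves a plain comparison of responder proportions. Computing the gain from each person's own baseline does not adjust for baseline: people who start lower tend to gain more when the correlation between visits is below 1. If the pilot and CAP groups start from different distances, part of the difference in responder rates would reflect that and not protein. The protocol calls a 50 m gain clinically meaningful, so readers are likely to look at this result.

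**Working it through.** **Inputs.** From section 14.4: 94 versus 27 analysable participants, within-subject correlation r = 0.70, 6MWT SD 55.8 m, two-sided alpha 0.05, 80% power. The documents give no mean gain, no responder rate and no baseline difference between cohorts; values for these below are assumptions. Section 14.4 does not say which visit the SD comes from; I use it for both visits.

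**The plan's own figure.** SD of change in SD units = √(2(1 − 0.70)) = 0.775. √(1/94 + 1/27) = 0.2183. Detectable difference = (1.960 + 0.842) × 0.775 × 0.2183 = 0.474 SD, against the stated 0.475. The plan's figure is therefore consistent with an unadjusted comparison of change. It concerns continuous distance; no figure is stated for the responder outcome.

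**Case A: 4-month rows only.** t4 equals 1 in every row, so it duplicates the intercept, and X·t4 duplicates X. The design matrix has rank 2 for four coefficients. Only a + b2 and b1 + b3 can be estimated; b3 cannot be separated from b1.

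**Case B: Y(0) = 0 for everyone.** The design has rank 4. The fit gives a = b1 = 0 exactly, and the baseline variance is 0, so the unstructured covariance does no work. For an illustrative data set with 28/94 and 12/27 responders:

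- raw difference = 0.4444 − 0.2979 = 0.1466
- SE = √(0.2979 × 0.7021/94 + 0.4444 × 0.5556/27) = 0.1066
- fitted b3 = 0.1466, robust SE 0.1066

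The GEE reproduces the unadjusted two-proportion result. In one fit the software returned no SE for the intercept; the SE of b3 was unaffected.

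**Dependence on starting distance.** Take bivariate normal distances with equal SDs and no treatment effect. The change has SD 0.775 × 55.8 = 43.2 m and regresses on baseline with slope −(1 − 0.70) = −0.30. A group starting d metres lower therefore has an expected gain 0.30·d larger, and

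P(gain ≥ 50) = 1 − Φ((50 − gain − 0.30·d)/43.2).

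With an assumed mean gain of 35 m in the comparator:

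| Pilot starts lower by | P in PUSH | P in pilot | Spurious difference |
|---|---|---|---|
| 15 m | 1 − Φ(0.347) = 36.4% | 1 − Φ(0.243) = 40.4% | +4.0 points |
| 30 m | 36.4% | 1 − Φ(0.139) = 44.5% | +8.1 points |

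For assumed gains from 20 to 60 m the ranges are +3.4 to +4.1 points (15 m) and +7.0 to +8.2 points (30 m). A simulation of the crude comparison (1,500 replicates per shift, slope about 0.7, gain 35 m) gave +3.9 and +8.3 points. Adjusting for baseline 6MWT reduced these to 0.0 and 0.4 points.

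**Same inputs, continuous 6MWT.** The planned b3 is biased by 0.30 × 15 = 4.5 m or 0.30 × 30 = 9.0 m. Its SE is 43.2 × 0.2183 = 9.44 m, so the bias is 0.48 or 0.95 SE. For the responder outcome the SE is about 0.107 for 15 m and 0.108 for 30 m, so the bias is about 0.37 or 0.75 SE.

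**The case against.** Four objections deserve an answer.

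*The model can be fitted.* A reader might infer from the missing baseline value that no estimate is obtainable. That goes too far. Non-identification applies only if no baseline value is supplied. With zeros at baseline, b3 and its robust SE form a valid crude risk difference. This objection stands.

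*Other outcomes are no better protected.* It is tempting to say that for continuous outcomes the baseline row takes care of baseline imbalance, and that only this outcome loses that protection. The documents do not support this. For continuous 6MWT, b3 is a difference in mean change with no covariates, and it carries the same regression-to-baseline bias, slightly larger relative to its SE. The responder definition already subtracts baseline, as b3 does. This objection also stands: moving the responder outcome to another model does not repair the wider lack of adjustment.

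*The outcome is minor.* Section 9.4 ranks it tertiary, section 14.2 calls it one of several potential outcomes, and no sample-size statement rests on it. It should not be presented as the trial's key clinical result. That limits the importance of the point but does not supply the missing analysis.

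*The sizes are hypothetical.* No cohort difference is documented; 30 m is 0.54 SD (30/55.8), a large imbalance. The bias is also modest beside what this outcome could detect: at 94 versus 27 with 80% power, about 28 to 30 points for assumed PUSH responder rates of 20% to 50%. That detectable difference comes from the sample sizes and the dichotomy. It gives scale and is not evidence of a fault in the model.

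**Conclusion.** The point holds in a limited form. The plan places a once-per-person binary outcome under a model that needs two values per person. Depending on an unstated coding choice, b3 is either not identified (rank 2 of 4) or equals the crude 16-week risk difference, and in neither case is starting distance adjusted for in a non-randomised comparison.

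The possible bias is about 4 points for a 15 m cohort difference and about 8 points for 30 m. This rests on SD 55.8 m at both visits, r = 0.70, normality, an assumed 35 m gain, no treatment effect, and the same dependence of change on baseline in both cohorts. The direction would reverse if the pilot group started higher. Whether any imbalance exists cannot be known from the documents.

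The link between outcome and model is a reading of section 14.2, which lists the outcome there and offers no other method. Given the outcome's rank and the moderate size of the bias, this is a worthwhile correction and not a threat to the primary analysis.

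**What to change.** In Protocol section 14.2 and the SAP, take the responder outcome out of the two-time-point GEE. State that the 16-week indicator will be analysed with one row per person, on group and baseline 6MWT, and that a baseline-adjusted (standardised) risk difference will be reported with robust SEs and the missing-data weights already planned in section 14.3. A logistic model with standardisation or a linear probability model would both serve; name one in advance.

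The cost is two sentences and a little extra analysis. No new data are needed: section 10.1 makes the six-minute walk a required baseline measure for every pilot participant, and the CAP baseline distance is already needed to compute the gain. Adjustment removes only the part of a cohort difference that measured starting distance explains.

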14.3 Missing Data

By design, there will be no missing data at baseline because only participants with complete baseline data will be randomized. At follow-up, scores for scales that have published rules for handling missing scale items (e.g., the CES-D and the SF-36) will be calculated using those rules. All other scales will be considered missing if any part of the scale is missing. To correct for potential selection bias from missing data, we will perform a weighted estimating equations (WEE) analysis.¹⁶⁹ This method involves two steps. First the probability of being observed (not missing) is calculated as a function of predictors of missingness. Next the relationship of treatment group to outcome is assessed using the inverse probability of being observed as a weight in the GEE model. WEEs are advantageous because a) they are consistent with the ITT principle because participants with missing data are included in the analysis through the estimated weight, and b) unlike other methods for addressing missing data, they can be performed in conjunction with marginal structural modeling by multiplying both weights together.

